This is a concurrently controlled trial. Study participants will be randomly selected from those participating in the ongoing, longitudinal +BHN study at 2 sites in Montreal (The Montreal Chest Institute and L'Actuel Medical Clinic). This CIHR Team Grant-supported observational, prospective cohort study is enrolling consecutive patients attending 5 HIV clinics across Canada for a total sample of 900, followed every 9 months for 27 months. Inclusion criteria are: age 35 y or older, HIV infection for at least 1 year, able to communicate in English or French and capable of providing informed consent. Exclusions are presence of dementia, life expectancy < 3 y, other neurological disorder including active opportunistic CNS infection, psychotic disorder, current substance dependence or abuse, and Hepatitis C requiring interferon therapy during the study period. Montreal sites will enroll 350 participants, which should provide an adequate pool for recruitment to this sub-study.

The GMT intervention will be tested in a randomly selected sub-group (N=30) of this cohort who meet the following additional criteria: over age 45, subjective complaints of cognitive difficulties, and performance on objective computerized cognitive tests that falls at or below the 50th percentile of performance in the cohort as a whole (as measured by the cohort study's primary outcome, a combination of self-report and performance items called the Brief Cognitive Ability Measure [B-CAM] (17)). The concurrent control group will be comprised of those eligible for GMT but not randomly selected.

Procedure

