Participants will be recruited at the time of their routine +BHN study visit, at which comprehensive information about their current health status, function, quality of life, cognitive concerns, and cognitive performance is already being gathered. Following informed consent, all participants will complete a short set of neuropsychological tests and questionnaires that have been shown to be sensitive to the effects of GMT [Sustained Attention to Response Task-SART (18),Tower of London (19), and Dysexecutive Questionnaire-DEX (20)] immediately, or at a visit arranged for this purpose, separate from the +BHN main study. Participants will then begin GMT, as described below. Within 4 weeks of completing the GMT program, they will be asked to repeat the neuropsychological testing and complete additional tests which form part of the standard +BHN visit at a second study visit, coincident with the +BHN study visit if timing permits.

Intervention

The standard GMT program lasts 9 weeks and involves 9 weekly 2-hour small group sessions led by a trained therapist. It follows a manualized program that teaches participants a series of techniques to build attention and executive function, and shows them how to implement these techniques in their everyday life. The small group sessions allow individualization of the training to show how it can be applied to

meet the particular challenges reported by participants, and explicitly encourage participants to share their challenges and successes with others in the group to promote learning and engagement with the program. The sessions are reinforced with homework, in which participants practice what they have learned. Sessions will be audiotaped for later review by the trainer and/or study investigators to ensure adherence to the intervention manual. The material, including homework, is provided in a workbook that participants use throughout the training, and keep for later reference.

TREATMENTS

There are no pharmacological treatments involved in the current study.

STUDY EVALUATIONS/PROCEDURES

Informed Consent

The subject will be asked to read and sign the approved informed consent form prior to any assessments being performed. Sufficient opportunity will be given to discuss the study and consider the information in the consent process prior to agreeing to participate. The original signed informed consent form will be retained in the subject's study files and a copy will be provided to the subject.

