Subject Identification Number Assignment

Subject Identification (ID) numbers assigned for the core platform will be used for this sub-study.

DETAILS OF STATISTICAL ANALYSIS

Analysis and Sample Size

The feasibility and acceptability of the GMT will be evaluated in the whole group (N=30) based on the proportion of GMT sessions attended, the proportion of the homework completed, and the overall level of satisfaction with the program, as determined by an anonymous questionnaire filled out by the participants at the end of the intervention.

The potential impact on cognition of GMT will be evaluated in two ways: (i) a within-person analysis of change in cognitive outcomes after all persons have completed the GMT program; and, for exploratory purposes, (ii) a between group comparison contrasting change in cognitive outcomes between the GMT group and the concurrent control group assessed in the main study.

For all analyses, the B-CAM (performance measure) will be the primary cognitive outcome and a global outcome response will be based on changes in the B-CAM and on four secondary cognitive outcome measures: SART, Tower of London, Dysexecutive Questionnaire-DEX and PDQ.

For the within-person analysis, change from pre-to post will be calculated for each person and a 95% confidence interval (CI) around the mean change will be calculated. A 95% CI that excludes 0 indicates statistically significant change. A sample size of 30 will provide 80% power to detect an average standardized response mean (effect size for change) of 0.38, within the reported range for GMT in other conditions. However, average change is not very interpretable as this average change can occur in many ways including no change for a lot of people and large change for a few, or even deterioration for some. To provide a more interpretable estimate of treatment impact, an overall effect will also be reported, based

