on the proportion of individuals who improved at least 0.5 SD on one of the cognitive outcome measures. A change of 0.5 SD is considered clinically relevant (21). For this analysis, generalized estimating equations (GEE) will be utilized to adjust for a possible correlation between the different measures. The outcome will be the binary response for each of the five cognitive outcomes, and the analysis yields an estimated charge proportion adjusted for non-independence. Having five outcome measures increases the number of observations available for analysis by a factor of 1.8, termed the design effect. The design effect (22) is a function of the number of measures (here m-1) and the correlation between measures (estimated at 0.2). Hence the number of observations effectively available for analysis is 30 x 1.8 or 54. With this sample size, the 95% CI will exclude a low responder proportion (20%) as long as the responder proportion is greater than 28% (www.vassarstats.net).

For the between-group analysis, 30 people in the intervention group and a concurrent control group of 100 (with five outcome measures, the effective sample size is inflated by the design effect of 1.8). Thus, using all measures, the sample would provide 80% power to detect an effect size of 0.4 (0.4 of a SD). For this analysis, generalized estimating equations (GEE) for a continuous outcome will be utilized to adjust for a possible correlation between the different measures. Each measure will be transformed onto a 0 to 100 scale for permit a global intervention effect to be estimated.

REFERENCES

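### The between-group power claim (80% at 0.4 SD) counts five measures in both groups, but three are never scheduled for controls; on B-CAM alone the detectable effect is 0.59 SD

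*Combined protocol and SAP*

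**What the plan says.** Analysis and Sample Size names B-CAM as the primary cognitive outcome and SART, Tower of London, DEX and PDQ as secondary, for every analysis. Its second analysis of cognition is given as "for exploratory purposes, (ii) a between group comparison contrasting change in cognitive outcomes". The comparator there is described as "the concurrent control group assessed in the main study". The model is a GEE over all measures, each rescaled to 0–100. For 30 GMT participants and 100 controls it says "with five outcome measures, the effective sample size is inflated by the design effect of 1.8", and concludes: "Thus, using all measures, the sample would provide 80% power to detect an effect size of 0.4 (0.4 of a SD").

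Study Design defines the comparison group: "The concurrent control group will be comprised of those eligible for GMT but not randomly selected". It also identifies B-CAM as the cohort's "primary outcome, a combination of self-report and performance items called the Brief Cognitive Ability Measure".

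Procedure gives SART, Tower of London and DEX to all participants after sub-study consent, either at once or at a visit outside the main study. The next sentence reads "Participants will then begin GMT, as described below". The repeat assessment falls within 4 weeks of finishing GMT, and there these tests are listed apart from those belonging to the standard +BHN visit.

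**The concern.** The inflation by 1.8 is justified only if each person in each group contributes change scores on five measures. The text places three of the five in a sub-study assessment taken by people who go on to GMT, with a repeat timed from the end of GMT. Controls have no such end point. Because the analysis contrasts change, even a baseline test in controls would not supply the outcome.

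This is the only analysis with a control group, and the Study Hypothesis is framed as a comparison with one. The Clinical Significance section says the results will inform a full randomised trial. If the achievable power is well below the stated 80%, a null between-group result could be read as stronger evidence against a 0.4 SD effect than it is.

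There is also a modelling risk. The terms of the GEE are not given. Without a term for measure, tests held only in the GMT group would enter the pooled group contrast, so differences between instruments could appear as a group effect.

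**Working it through.** **Inputs.** From Analysis and Sample Size: 30 GMT and 100 controls, m = 5 measures, correlation ρ = 0.2, 80% power, effect in SD units. Sidedness is not stated for this comparison. I take two-sided 5%, in line with the rule for the within-person analysis ("A 95% CI that excludes 0 indicates statistically significant change"). The plan's within-person figure of 0.38 supports this: (1.960 + 0.842)/√54 = 0.381.

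**Formula.** Detectable effect ≈ (1.960 + 0.842) × √(1/n₁ + 1/n₂). The results below use the noncentral t, which differs little.

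**Step 1: the plan's figure.** The factor is 1 + (5 − 1) × 0.2 = 1.8, so the effective sizes are 30 × 1.8 = 54 and 100 × 1.8 = 180. Then 2.802 × √(1/54 + 1/180) = 0.435 (t: 0.44), with 73% power at exactly 0.4. I treat this as rounding to 0.4. Inflating the GMT group alone (54 vs 100) gives 0.48, so on a two-sided test the stated figure needs five measures in both groups.

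**Step 2: which measures are shared.**
- B-CAM: yes, as the cohort's primary outcome.
- PDQ: named only in the analysis section, so its availability in controls is an assumption.
- SART, Tower of London, DEX: no schedule for controls anywhere.

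**Step 3: power on shared measures.** The plan multiplies n by 1 + (m − 1)ρ. The conventional multiplier for m equally correlated measures is m/[1 + (m − 1)ρ]. Both are shown.

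| Measures in both groups | Multiplier | Effective n | Effect at 80% power | Power at 0.4 SD |
|---|---|---|---|---|
| B-CAM alone | 1 | 30 vs 100 | 0.59 | 48% |
| B-CAM + PDQ, plan's factor | 1.2 | 36 vs 120 | 0.54 | 55% |
| B-CAM + PDQ, conventional | 2/1.2 = 1.67 | 50 vs 167 | 0.45 | 70% |
| B-CAM + PDQ, ρ = 0 | 2 | 60 vs 200 | 0.41 | 77% |
| All five, plan's factor | 1.8 | 54 vs 180 | 0.44 | 73% |
| All five, conventional | 5/1.8 = 2.78 | 83 vs 278 | 0.35 | 89% |

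Like for like, dropping from five measures to two moves the detectable effect from 0.44 to 0.54 (plan's factor) or from 0.35 to 0.45 (conventional).

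**Step 4: can 0.4 SD be reached?** It needs a multiplier of 2.14. Two measures give at most 2.0, and only if uncorrelated. With the conventional factor, ρ from 0.1 to 0.5 gives 0.43 to 0.51. More controls do not rescue B-CAM alone: with unlimited controls the limit is 2.802/√30 = 0.51.

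**Sensitivity.** One-sided 5% gives 0.52 for B-CAM alone, and for two measures 0.40 (conventional) or 0.47 (plan's factor). The Protocol Summary gives a sample size of 60; if that meant 30 + 30 (an assumption), B-CAM alone would give 0.74.

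**The case against.** The +BHN battery is never listed, so one cannot prove that controls lack the three tests. Some wording points towards testing them: the five measures are named for all analyses, Procedure speaks of all participants, and the summary and hypothesis mention a wait-list, whose members could later begin GMT. This is why the finding is an inference. But none of that wording gives controls a repeat assessment, and the description of controls as assessed in the main study, with 100 of them, fits the cohort reading better.

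The figure of 0.59 SD is the least favourable case, and it concerns one measure where the plan's sentence concerns a pooled effect. That is fair, and the two-measure figures belong beside it. The gap is then smaller. With the conventional factor, 0.45 is close to the 0.44 that I accept as rounding, and at ρ = 0.1 the two-measure figure is 0.43. A one-sided test would reach 0.40, but nothing in the document states one. The like-for-like loss of about 0.10 SD remains under either factor.

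The consequence is also limited. The comparison is labelled exploratory, feasibility is the first objective, the within-person analysis is untouched, B-CAM is available in both groups, and no decision rule hangs on this test.

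**Conclusion.** The concern holds. As documented, the control group does not have five measures with change scores, so the stated 80% power at 0.4 SD is not supported. On the one measure certain to be shared, the detectable effect is 0.59 SD and power at 0.4 SD is 48%. If controls also have PDQ, it is 0.45 to 0.54 SD at correlation 0.2, depending on the factor. These figures assume a two-sided 5% test and 30 vs 100 with complete data.

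The conclusion rests on reading Procedure as describing GMT participants only. If controls do take all five tests before and after, the conventional factor gives 0.35 SD and the plan's claim is met. Confidence is medium for that reason. The point should be fixed, but it does not threaten the study's main analyses.

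**What to change.** State which of the five measures controls have, and at which visits. Then choose one of two routes.

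**A. Restrict the comparison to shared measures.** Make B-CAM primary, with PDQ secondary if controls have it, and report SART, Tower of London and DEX for the GMT group only. Replace the power sentence with: *For this exploratory comparison, 30 GMT and 100 control participants give 80% power (two-sided 5%) to detect 0.59 SD in B-CAM change.* If PDQ is available, add 0.45 SD for the two pooled, naming the factor m/[1 + (m − 1)ρ] and ρ = 0.2. This costs only wording and a less favourable number.

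**B. Test controls on the three instruments at both time points.** Restate the power with the factor named (0.35 SD at ρ = 0.2 with the conventional one). This costs about 100 × 2 = 200 extra test sessions.

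Under either route, specify a term for measure in the GEE. Separately, reconcile the Protocol Summary's sample size of 60 and waitlist control with the 30 GMT participants and 100 concurrent controls in the analysis section.
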